- 1- Forty obese infertile patients with poly cystic ovarian syndrome.
- 2- Their ages will be ranged between 20-35 year old.
- 3- Their body mass index will be ranged from 30-40 kg/m².
- 4- All of them are married women.

Limitations:

This study will be limited to the following criteria:

- 1- Psychological status.
- 2- Cooperation of the patients may affect the result of the study.
- 3- Environmental factors which may have affected the patient's response.
- 4- The daily effort may affect the result of the study.

Null Hypothesis:

It will be hypothesized that, there is no difference between the effect of ultrasound cavitation and electroacupuncture on sex hormones in obese infertile patients with poly cystic ovarian syndrome.

Basic assumptions:

It will be assumed that:

- 1- All patients will show adequate cooperation with study procedure.
- 2- All patients will follow the instructions that will be given to them.
- 3- Clinical methods of evaluation will be reliable and valid.
- 4- Results obtained from this study will be of value in physical therapy.

CHAPTER II

LITERATURE REVIEW

PCOS is the major endocrine disorder affecting females in age of reproduction and is considered to be the most common cause of an ovulatory infertility. According to diagnostic criteria, PCOS affects 12-21% of women in child bearing period of life; however, many cases are undiagnosed (**Stabile et al., 2014**). It represents a condition in which an estimate of 10 small cysts of a diameter ranging between 2 and 9 mm develop on one or both ovaries and/or the ovarian volume in at least one ovary exceeds 10 ml (**Balen and Rajkowha, 2003**).

Although it was previously considered as a disorder of adult women, recent evidence suggests that PCOS is a lifelong syndrome, manifesting since prenatal age. In fact, according to the Rotterdam diagnostic criteria, the prevalence of PCOS, in adolescents varies between a minimum of 3% (**Hashemipour et al., 2004**) and a maximum of 26% (**Driscoll, 2003**). However, the prevalence of the disease in children is still considered unknown (**Kamangar et al., 2015**).

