Standard dietary management of obesity and related comorbidities is a nutritionally adequate, low fat (approximately 30% of energy, saturated fat approximately 10%), moderate protein (approximately 15%) and high carbohydrate intake (approximately 55%), with increased fiber-rich wholegrain breads, cereals, fruits and vegetables and moderate regular exercise. A moderate energy reduction diet (500 to 1,000 kcal/day reduction) reduces body weight by 7% to 10% over a period of 6 to 12 months (**Dansinger et al., 2005**).

2- Life style modification:

Lifestyle change is first line treatment in an evidence-based approach in the management of the majority of PCOS women who are overweight (**Moran et al., 2009**).

Furthermore, prevention of excess weight gain should be emphasized in all women with PCOS of both normal or increased body weight. As little as 5% to 10% weight loss has significant clinical benefits improving psychological outcomes, reproductive features (menstrual cycle, ovulation and fertility) and metabolic features (insulin resistance and risk factors for CVD and DM2) (**Galletly et al., 1996**). Evidence

shows that lifestyle change with small achievable goals results in clinical benefits even when women remain in the overweight or obese range **(Wahrenberg et al., 1999)**.

3- Exercise:

Incorporating simple moderate physical activity including structured exercise (at least 30 min/day) and incidental exercise increases weight loss and improves clinical outcomes in PCOS compared to diet alone. Exercise alone also improves clinical outcomes **(Poehlman et al., 2000)**.

Aerobic exercise for 12 weeks is an effective method to decrease visceral fat, waist circumference, in obese subjects with T2DM even without weight loss. Frequent aerobic exercise has been shown to increase HDL-C levels by approximately 5% as early as 2 months from start of regular exercise in sedentary but otherwise healthy individuals **(Dekker et al., 2007)**.

4- Medical treatment:

A- Oral contraceptive pills (OCP):

OCP are the most commonly used medications for the long-term treatment of women with PCO and have been recommended by the Task Force and the Endocrine Society **(Legro et al., 2013)**, the Australian Alliance **(Misso et al., 2014)** and the PCOS Consensus Group as first-line treatment for hyperandrogenism and menstrual cycle irregularities in women with PCOS **(Fauser et al., 2012)**.

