- 3- Concomitant cardiovascular disorders.
- 4- Respiratory, renal and liver dysfunction.
- 5- Tubal adhesions as well as uterine abnormalities.

All patients will be divided randomly into two equal groups (A&B).

Group A:

It will consist of twenty obese infertile patients with PCO who will be treated by ultrasound cavitation on the abdomen, 2 times per week for 3 months with medical treatment in addition to hypocaloric diet (1200 kcal/day) for 3 months.

Group B:

It will consist of twenty obese infertile patients with PCO who will be treated by electroacupuncture, 3 times per week for 3 months with medical treatment in addition to hypocaloric diet (1200 kcal/day) for 3 months.

All patients will be given a full explanation of the study protocol and consent form will be signed by each woman before participating in the study, the purpose and nature of the study will be explained to all patients (**Appendix I**).

II- Instrumentations:

1- Recording data sheet (Appendix II).

2- Standard weight height scale:

It will be used to measure weight and height to calculate the body mass index (BMI) for each woman.

3- Tape measurement:

It will be used to calculate the waist/hip ratio.

4- Test tubes:

Sterilized test tubes will be used to collect the blood samples from obese infertile patients with PCO.

5- Kites:

They will be used for assessment of serum progesterone level, testosterone, LH and FSH hormones.

6- Abdominal ultrasonography:

It will be used for measuring ovulation rate.

7- Focused ultrasound cavitation:

Fat cavitation, biCAVI (Ultimate). It will be used to apply the treatment procedure for all patients in group A.

8- Electro acupuncture:

It will be used to apply the treatment procedure for all patients in group B.

III- Procedures:

A-Evaluative procedures:

1. Weight and height measurements:

Weight and height measurements will be measured while the patient is wearing a thin layer of clothes to calculate the BMI according to the following equation before and after treatment for both groups (A&B):

$$\text{BMI} = \text{weight/height}^2 \text{ (kg/m}^2\text{)}.$$

2. Waist and Hip Ratio:

- It must be taken in order to accurately measure obesity rather than just visually inspecting of naked body (reference of female measurements : minimal waist circumference >88 cm and waist-hip ratio >0.85).

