- Then the cavitation head will be moved very slowly on each abdominal segment in a small circular movement for 5 minutes.
- After finishing the focused ultrasound of the 6 segments of the abdomen, the skin will be cleaned with cotton. The total duration of the ultrasound treatment session on the 6 segments of the abdominal area will be 30 minutes.

4- Electroacupuncture:

- Each patient in group B will be treated by electroacupuncture, three sessions per week for 3 months.
- The electrodes must be applied on the effective acupuncture points in somatic segments that innervates the ovary and uterus (Th12-L2 and S2-4).

- Electric stimulation with low frequency 2Hz, pulse width 0.5ms for 30minutes will be chosen.

Statistical analysis:

Data will be collected and statistically analyzed using:

- Descriptive statistics including mean and stander deviation.
- Unpaired t-test will be conducted for comparison of mean values of pre and post-treatment between groups.
- Paired t-test will be conducted for comparison between pre and post-treatment mean values in each group.
- Level of significance, the degree of significance will be selected at 5%, P value <0.05 will indicate non-significant results, P value > 0.05 will indicate a highly significant result.

REFERENCES

Ascher B. 2010: Safety and efficacy of ultra-shape contour I treatments to improve the appearance of body contours. : Multiple treatments in shorter intervals. *A.S.J.*, 30 (2): 217-24.

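### The planned paired pre/post t-test in each group measures the whole package of device, diet and medical treatment, so it cannot show that cavitation or electroacupuncture works

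*Protocol*

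**What the plan says.** In Chapter III, Group A is defined by cavitation ("It will consist of twenty obese infertile patients with PCO who will be treated by ultrasound cavitation on the abdomen") and Group B by electroacupuncture ("It will consist of twenty obese infertile patients with PCO who will be treated by electroacupuncture"). Each definition goes on to add the same background: "with medical treatment in addition to hypocaloric diet (1200 kcal/day) for 3 months". The treatment procedures confirm that diet and medical treatment are to be the same in both groups. The drug is not named.

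Under Blood analysis, samples are taken before and after treatment only. The protocol describes no period on diet or drug before the baseline sample, and no group that receives them without a device.

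The Statistical analysis section lists a between-group test ("Unpaired t-test will be conducted for comparison of mean values of pre and post-treatment between groups") and a within-group test ("Paired t-test will be conducted for comparison between pre and post-treatment mean values in each group"). One significance level covers both: "the degree of significance will be selected at 5" per cent. Nothing there limits the paired test to description.

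The single Null Hypothesis concerns only the contrast between devices: "there is no difference between the effect of ultrasound cavitation and electroacupuncture on sex hormones".

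**The concern.** A paired test asks whether the mean changed over 3 months. In either arm that change has at least four possible sources: the device, the diet, the medical treatment, and time or regression to the mean. The design gives no means of separating them within an arm.

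The protocol's own literature review gives reason to expect change without any device. On lifestyle it says: "As little as 5% to 10% weight loss has significant clinical benefits improving psychological outcomes, reproductive features (menstrual cycle, ovulation and fertility". On medical treatment it describes oral contraceptives as lowering LH and free testosterone, and metformin as lowering raised androgens in obese adolescents with PCOS and impaired glucose tolerance. In its section on sex hormones it warns that testosterone is hard to interpret in women on oral contraceptives.

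What is at stake is the reading of the results. If both arms improve significantly and the between-group test is not significant, it is easy to conclude that both devices work. If only one arm reaches significance, it is easy to conclude that one works and the other does not. This design supports neither conclusion, and both patterns can arise when the devices do nothing.

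**Working it through.** The protocol gives 20 per group without an effect size, SD or power, so there is no stated figure to reproduce. The check asks how often the paired test would be significant if the devices had no effect at all.

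**Inputs**
- n = 20 per arm (Group A and Group B definitions).
- α = 0.05 (Statistical analysis). Sidedness is not stated; two-sided is assumed. P below 0.05 is read as significant in the usual way. The same bullet words the rule in the opposite direction, which is a separate matter.
- Device effect = 0 in both arms (assumed for the check).
- Shared shift d from diet, drug and time, in SDs of the paired differences. This is assumed over a range, because the protocol gives no figure for it.

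**Formula.** With 19 degrees of freedom the critical value is 2.093 and the noncentrality is λ = d√20. The chance that one arm is significant is

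p = 1 − F(2.093; 19, λ) + F(−2.093; 19, λ),

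where F is the noncentral t distribution function. For a given d the arms are independent, so both are significant with probability p², at least one with 1 − (1 − p)², and exactly one with 2p(1 − p).

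| d | λ | A given arm | Both arms | At least one arm |
|---|---|---|---|---|
| 0 | 0 | 5.0% | 0.3% | 9.8% |
| 0.2 | 0.89 | 13.6% | 1.8% | 25.3% |
| 0.3 | 1.34 | 24.7% | 6.1% | 43.3% |
| 0.5 | 2.24 | 56.5% | 31.9% | 81.0% |
| 0.8 | 3.58 | 92.4% | 85.4% | 99.4% |
| 1.0 | 4.47 | 98.9% | 97.7% | about 100% |

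At d = 0.5 exactly one arm is significant in 2 × 0.565 × 0.435 = 49% of trials, although the devices are identical by construction.

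**Between-group comparison.** An unpaired t-test on change scores was simulated (100,000 runs, same shift in both arms, no device difference). It rejected in 5.0%, 5.0%, 5.0% and 5.1% of runs for d = 0, 0.3, 0.5 and 0.8. A shared shift cancels there.

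**Diet alone, using the protocol's figures for weight.** The Hypocaloric diet section cites a 7% to 10% weight loss over 6 to 12 months for a moderate energy-reduction diet. If loss is linear and the trial diet behaves alike (both assumed), 3 months gives between 7 × 3/12 = 1.75% and 10 × 3/6 = 5.0%. With an assumed SD of change of 3 to 5 percentage points, d runs from 1.75/5 = 0.35 to 5.0/3 = 1.67. The paired test on weight is then significant in 32% to about 100% of trials from diet alone.

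**The case against.** The strongest case on the other side has five parts.

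1. **The protocol never claims what is feared.** The aim, the problem statement and the null hypothesis all concern the difference between devices, and the unpaired test is listed first. A reader might infer that the sponsor will credit each device with its own arm's change. The protocol does not say so. This stands: the risk is one of misreading. It remains a real risk, because the arms are named by device and nothing restricts the interpretation.

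2. **Randomisation takes care of shared co-treatment.** A reader might infer that the diet and drugs confound the trial's main comparison. They do not, provided they really are the same in both arms. This stands in full, and it confines the point to the within-group tests.

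3. **The percentages are power, not error.** A reader might set 32% to 98% against 5% and call it a false-positive rate. That is wrong. Under the assumed shift a real change exists, so the paired test is right to detect it. The error arises only if the change is then attributed to the device. The range also depends on the assumption: at 0.2 to 0.3 SD, both arms are significant in only about 2% to 6% of trials.

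4. **The size of the co-treatment effect is not established.** The drug is unnamed and its start relative to baseline is not given, so its contribution is conditional. The statement on weight loss names cycle, ovulation and fertility rather than testosterone or LH/FSH ratio, and it applies from 5% loss, which is the top of the 3-month range above. This stands, and it is why the shift is shown as a range. That the diet runs through the interval in both arms does not depend on it.

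5. **The SAP may label the paired tests descriptive.** It may. But the protocol itself specifies these tests, at the same significance level as the between-group test and without limit. The point is about a stated analysis, not about missing detail.

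**Conclusion.** The point holds in a limited form. The paired tests in each group answer no question that the trial poses, and a significant result cannot be assigned to cavitation or electroacupuncture. The between-group comparison remains sound for the stated null hypothesis.

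The illustrated chance of a significant package change that could be misread as a device effect is about 14% to 99% for a given arm and about 2% to 98% for both. This rests on a shared shift of 0.2 to 1.0 SD, no device effect, 20 completers per arm and a two-sided 5% test. It is an illustration, because the protocol does not fix the shift. It does not predict how the sponsor will report.

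Severity is moderate: the answer to the trial's only hypothesis does not change, but the message drawn from the results could.

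**What to change.** In Statistical analysis:
- State that the between-group comparison, of change or of the baseline-adjusted post-treatment value, is the sole basis for conclusions about the devices.
- Replace the within-group paired tests by the mean change with its 95% CI in each group, labelled as descriptive of the whole package (device, diet and medical treatment).
- State that neither a within-group change nor a non-significant between-group result will be reported as evidence that either device is effective.

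The cost is wording only. Treatment, sampling and sample size stay as they are. The sponsor gives up the option of claiming efficacy for each device from its own arm, a claim that this design could not support in any case.

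### The significance rule is stated backwards: P below 0.05 is called non-significant and P above 0.05 highly significant, so followed as written every t-test in the protocol gives the opposite conclusion

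*Protocol*

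**What the plan says.** The last bullet under Statistical analysis in Chapter III of the protocol does two things. It fixes the level ("the degree of significance will be selected at 5" per cent), and it then says how P values are to be read: "P value <0.05 will indicate non-significant results, P value > 0.05 will indicate a highly significant result".

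The bullets just above it name the tests to which this reading applies:

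- Between groups: "Unpaired t-test will be conducted for comparison of mean values of pre and post-treatment between groups".
- Within groups: "Paired t-test will be conducted for comparison between pre and post-treatment mean values in each group".

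The Null Hypothesis section states that "there is no difference between the effect of ultrasound cavitation and electroacupuncture on sex hormones" in the study population. No other part of the protocol gives a decision rule or corrects this one.

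**The concern.** A significance level of 5% means that the null hypothesis is rejected when P falls below 0.05. The protocol attaches the labels the other way round, so the bullet contradicts itself. Both halves are reversed consistently, so one lost or misread character does not account for it.

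A different kind of hypothesis does not account for it either. The null is the conventional one of no difference. Even in an equivalence or non-inferiority design, a small P value would still be the significant one.

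The rule decides whether that null is rejected, and it governs every comparison of LH/FSH ratio, testosterone and progesterone. Applied literally, the trial would claim a difference between ultrasound cavitation and electroacupuncture when the data show none, and would deny one when the data show it clearly.

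There are two smaller defects in the same sentence. The label highly significant hangs on the single 5% cut-off, with no stricter threshold behind it. And P exactly equal to 0.05 falls in neither category.

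**Working it through.** **Inputs from the protocol**

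- Significance level 5%, and the decision rule as written (Statistical analysis).
- Unpaired t-test between groups and paired t-test within groups (Statistical analysis).
- Null hypothesis of no difference (Null Hypothesis section).
- Equal random allocation: "All patients will be divided randomly into two equal groups (A&B"). The Subjects section puts twenty women in each arm, so n = 20 per group and df = 2 × 20 − 2 = 38.

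**Assumptions.** The protocol states no effect size, SD or power target. The standardised differences d used in steps 3 and 4 are therefore assumptions, shown over a range. Tests are taken as two-sided and all 40 women as analysed.

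**Step 1: does the rule give the stated 5%?** Under the null, the P value of a t-test is uniform between 0 and 1.

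- As written: false-positive rate = Pr(P > 0.05) = 1 − 0.05 = 0.95.
- Labels exchanged: false-positive rate = Pr(P < 0.05) = 0.05.

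The stated 5% is not reproduced by the rule as written and is reproduced exactly once the labels are exchanged. A simulation of 100,000 unpaired t-tests with 20 per group and no true difference gave P > 0.05 in 0.9499 of runs and P < 0.05 in 0.0501. No run gave P exactly 0.05, so the two rules disagreed every time. Taking the tests as one-sided would not change this step, because P is still uniform under the null.

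**Step 2: the three hormone measures together.** The chance of at least one falsely significant result is 1 − Pr(all three P < 0.05).

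- If the three tests were independent: 1 − 0.05³ = 0.9999.
- They come from the same women, so independence is not assured. Whatever the dependence, Pr(all three P < 0.05) lies between 0 and 0.05, so the answer lies between 95% and 100%.

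**Step 3: what happens when there is a true difference.** Power of the unpaired t-test comes from the noncentral t distribution with df = 38 and noncentrality d × √(n/2) = d × √10 = 3.162 d. The chance of significance as written is 1 minus that power.

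| Assumed d (SD) | Noncentrality | Significant, labels exchanged | Significant, as written |
|---|---|---|---|
| 0 | 0 | 0.05 | 0.95 |
| 0.5 | 1.58 | 0.34 | 0.66 |
| 0.8 | 2.53 | 0.69 | 0.31 |
| 0.909 | 2.87 | 0.80 | 0.20 |
| 1.0 | 3.16 | 0.87 | 0.13 |

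Simulation agreed at d = 0.5 (0.338 and 0.662) and d = 0.8 (0.691 and 0.309). As written, the chance of declaring significance falls as the true effect grows. The value 0.909 SD is simply the difference that a correct 5% test with 20 per group detects 80% of the time; the rule as written would call it non-significant 80% of the time.

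**Step 4: precision, for reading a non-significant result.** The half-width of the 95% confidence interval for the difference in means is t(0.975, 38) × √(2/20) = 2.024 × 0.316 = 0.64 SD. A corrected result of P ≥ 0.05 would therefore still leave fairly large differences possible.

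**The case against.** The strongest reply is that this is an obvious slip. The bullet itself sets 5%, the null is conventional and the tests are ordinary t-tests, so the only sensible reading is that the two inequality signs were transposed. No competent analyst would report P = 0.60 as highly significant, and the 95% error rate is just 1 minus 5%, not a forecast of how the trial will behave. An analysis plan not shown here may also state the rule correctly.

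Much of this is fair. A transposition is very probably the explanation, and the 95% figure is conditional on the sentence being followed. The tabulated effect sizes are not in the protocol and serve only as illustration. The independence behind the 99.99% figure is not supported, which is why a range is given. The complaint about the word highly is minor, since it changes no decision once the signs are right.

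What does not stand is the inference that the sentence can be left alone. The point concerns something the protocol states wrongly, not detail left to an analysis plan. A correct analysis plan would contradict the protocol, which would still need amending. If nothing is changed, the analyst must either report reversed conclusions or depart silently from the one pre-specified rule.

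**Conclusion.** The concern holds. The protocol's decision rule is wrong as written and contradicts the 5% level in its own bullet. Followed literally, each t-test named in the protocol has a type I error of 95% against the stated 5%. That result needs only that P is uniform under the null; it does not depend on sample size or effect size. The loss of power for true differences depends on the assumed effect sizes, but the direction of the error does not. It should be corrected before any analysis because it is the only rule given and it determines the conclusion on the main hypothesis, even though the likely cause is no more than swapped signs.

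**What to change.** Replace the last bullet under Statistical analysis with wording such as:

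*Tests are two-sided at the 5% level. P < 0.05 is taken as a statistically significant difference; P ≥ 0.05 is taken as no statistically significant difference.*

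This restores the 5% error rate, assigns P = 0.05 to a category and drops the word highly. The essential change is the exchange of the two labels.

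It would also help to report each between-group difference with its 95% confidence interval, and to say that P ≥ 0.05 is not evidence that the treatments are the same. These additions may equally sit in the analysis plan. If an analysis plan exists, check that it states the same rule.

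Cost: one sentence in the protocol, with no additional patients or data. Making the change before results are examined keeps it from looking post hoc.
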